5.1 Regulatory framework

5.2 Research ethics approval and monitoring

5.3 Adverse events

5.4 Indemnity

5.5 Sponsor

5.6 Funding

5.7 Audit

5.8 Study Management

5.9 Publication policy

5.4 End of trial

6. References

1. Protocol summary

| | |
|----------------------------------|---|
| Title | A pilot randomised controlled trial of fortified Human Donor Milk (HDM), unfortified HDM, or Preterm Formula (PTF) in preterm babies, to make up any shortfall in the volume of Mother's Own Milk (MOM) |
| Study Centre | Chelsea and Westminster Hospital Neonatal Unit |
| Study Objectives | 
 1. To assess the feasibility of a multicentre trial addressing short term (Necrotising Enterocolitis and Bloodstream Infection) and long term (growth and metabolic) outcomes 2. To address the null hypothesis: there are no differences in total body adiposity, as measured by whole body MRI, between any groups of infants randomised to receive unfortified MOM+/-HDM, fortified MOM+/-HDM or MOM+/-PTF 3. To assess the macronutrient content of HDM given to each infant in the HDM arms by analysis of HDM samples |
| Study Design | Single centre unblinded randomised controlled trial |
| Study Population | 
Inclusion Criteria
 
 • Preterm infants born between 25+0 to 31+6 weeks gestational age 
Exclusion Criteria
 
 • Major congenital or life threatening abnormalities or congenital abnormalities that preclude early milk feeding • Inability to randomise infant within 48 hours |
| Intervention | 
Either
 
 1. HDM, fortified with standard commercial multicomponent breast milk fortifier, once enteral intake of 150ml/kg/d reached, to supplement MOM 
Or
 
 2. Unfortified HDM to supplement MOM |
| Comparator | PTF to supplement MOM |
| Target number of patients | 84 (28 in each group) |
| Randomisation | 
 • Using minimisation • Stratifying factors are: gestational age (25-27+6 w and 28-31+6 w), birth weight z score (<-1.28, >-1.28) and sex |
| Primary outcomes | 
 • Total body adiposity, as measured by whole body MRI, at term equivalent age |
| Secondary outcomes | 
 • Total body adiposity, as measured by whole body MRI at term plus 6 weeks corrected gestational age • Regional adiposity, as measured by whole body MRI • Non adipose tissue, as measured by whole body MRI • Anthropometry (weight, length, and head circumference) • Intrahepatocellular Lipid, as measured by magnetic resonance spectroscopy • Blood pressure • Stool and urine metabolomic profile • MicroRNA profile • Fasting blood Quantitative Insulin Sensitivity Check Index at term equivalent age |
| Duration of study | 
Recruitment: 18 months
 
End of trial: Up to 24 months
 |

2. Background

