2.4 Importance to the NHS

Infant nutrition studies involving randomisation, testing causality and unravelling biological mechanisms are rare. Yet infant nutrition is a cardinal candidate effector of long-term health. Current practice in feeding the preterm infant invariably involves the use of fortified Human Donor Milk or Preterm Formula. There are however no national standards or guidelines for enteral feeding of extremely preterm infants, and clinical practice is very variable.

Advocates of pasteurised HDM believe this is as efficacious as MOM in reducing two of the most feared conditions in newborn medicine, necrotising enterocolitis and bloodstream infection, and in improving long-term metabolic health. These result in major health services utilisation costs and a life-long burden of impairments on survivors.

An adequately powered trial is required to address these outcomes but poses two major hurdles, recruitment of large numbers of babies, and long-term follow-up. The organisation of NHS neonatal specialist care and the establishment of the Neonatal Data Analysis Unit that holds and archives national neonatal data at Chelsea & Westminster Hospital, and has received permission for the National Information Governance Board to link this to Hospital Episode statistics data, offers unique international opportunity to conduct this trial in the UK and achieve long term follow-up at low cost. Clarification of efficacy will advance clinical care, and enable economic evaluation and rational development of Human Milk Banking.

3. Aims and Hypothesis

Specific aims of this pilot trial are to:

A: Assess feasibility

- 1) test the acceptability of the trial design with parents and clinicians
- 2) test that recruitment to target is achievable, estimate consent and dropout rates
- 3) estimate the trial requirement for HDM from NHS Human Milk Banks
- 4) test that clinical outcome data can be retrieved from operational NHS electronic records, thus minimising the burden of data capture and facilitating the use of linked NHS records to achieve long-term follow-up at low cost.

B: Obtain data on the magnitude of effect at term equivalent age and again at term plus 6 weeks of age, on key mechanistic outcomes:

- 1) the primary outcome of total body adiposity, addressing the null hypothesis: there are no differences in total body adiposity, as measured by whole body MRI, between infants randomised to receive fortified MOM+/-HDM, unfortified MOM+/-HDM, or MOM+/-PTF.

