4.9.8 Magnetic Resonance Investigations (MRI and MRS)

Infants will undergo two magnetic resonance investigations, according to a well-defined and well established protocol (57-59). The first investigation will be as soon as possible after discharge. To investigate whether early feeding impacts on body composition

changes which persist beyond discharge, a second scan at around a corrected gestational age of term plus 6 weeks will be performed. This protocol has been used for over a decade in a large number of preterm and term infants. The MRI measurements are carried out during normal sleep without the need for sedation. All the MRI measurements (brain volume, body composition, and hepatic MRS) take a total of about 20-25 minutes. Both quantity and distribution of adipose and non-adipose tissue will be assessed. The infants will be monitored with pulse oximetry and a trained neonatal doctor will be present throughout the scan. Parents are invited to be present in the console room.

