Using our group's database of preterm infants at term age equivalent (July 2012), the mean (standard deviation) of directly measured total body adiposity, using whole body MRI is 0.677(0.243)l. Although the clinically relevant difference may be less than this, we have based our sample size on detecting a one standard deviation difference. A sample size of 22 infants in each group would enable us to detect a 0.243l difference in adiposity between groups with just over 80% power and at 5% significance level. Assuming 10% mortality prior to term and 10% drop out rate, 28 infants will be recruited in to each of the three groups or until 22 infants in each group has had their MRI and MRS at term age equivalent, a total of 66 scans. Thus, over a recruitment period of 18 months, with an estimated recruitment rate of 2-4 infants per month it is realised that the study will likely be underpowered for the outcome of total body adiposity. This sample size is based on single centre recruitment. In the eventuality of one or more centres being involved in the study, the following table has been constructed to demonstrate sample sizes and powers required for detecting a range of possible clinically significant differences in total body adiposity, for which the Bonferroni correction has been used for multiple testing.

Table 3. Power to detect possible clinically relevant differences in adiposity for different sample sizes; AT=adipose tissue; l=litre

| Total n | Power (%) to detect 0.096(l) diff in AT | Power (%) to detect 0.243(l) (1 sd) diff in AT | Difference (l) in AT at 80% power |
|---------|---|--|-----------------------------------|
| 60 | 12.8 | 78.1 | 0.249 |
| 66 | 14.1 | 82.4 | 0.237 |
| 75 | 16.1 | 87.5 | 0.222 |
| 90 | 19.6 | 93.1 | 0.203 |
| 96 | 21 | 94.7 | 0.197 |
| 105 | 23.1 | 96.4 | 0.188 |
| 120 | 26.8 | 98.1 | 0.176 |
| 135 | 30.4 | 99.1 | 0.166 |
| 150 | 34 | 99.6 | 0.157 |
| 165 | 37.6 | 99.8 | 0.15 |
| 180 | 41.2 | 99.9 | 0.144 |
| 210 | 48 | 100 | 0.133 |
| 225 | 51.3 | | 0.129 |
| 240 | 54.5 | | 0.125 |

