4.11.2 Statistical analysis

Outcomes will be analysed both for by intention to treat and as per protocol using multiple linear regression with adjustment for covariates where appropriate. Baseline covariates such as gender, gestational age, and birthweight z score, will be controlled for by randomisation stratification, while those such as ethnicity will be adjusted for. To address the null hypothesis differences between groups will be tested using ANOVA, with examination of the 3 pairwise differences for magnitude of differences. For the purposes of modelling randomised babies will be assigned to categories of overall intake (predominantly MOM, predominantly PTF, predominantly HDM). Results will be presented as estimates and 95% confidence intervals for differences in means.

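### Section 4.11.2 names no analysis linking the two scans, so the plan gives no estimate or confidence interval for how the arm difference changes between them

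*Combined protocol and SAP*

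**What the plan says.** Total body adiposity is measured by MRI twice. The value at term equivalent age is the primary outcome. The protocol summary (section 1) lists the later value as a secondary outcome: "Total body adiposity, as measured by whole body MRI at term plus 6 weeks corrected gestational age".

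Section 4.9.8 explains why infants are scanned again. The interest is in body composition "changes which persist beyond discharge, a second scan at around a corrected gestational age of term plus 6 weeks will be performed". Under sections 4.6 and 4.8.2 allocated feeding stops at 34+6 weeks and maternal choice follows, so both scans come after the intervention period.

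Aim B in section 3 is worded as estimation at each age: "Obtain data on the magnitude of effect at term equivalent age and again at term plus 6 weeks of age".

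Section 4.11.2 is the whole analysis plan. It says "Outcomes will be analysed both for by intention to treat and as per protocol using multiple linear regression with adjustment for covariates where appropriate", then "To address the null hypothesis differences between groups will be tested using ANOVA, with examination of the 3 pairwise differences for magnitude of differences", and mentions modelling by predominant milk intake. On reporting it says "Results will be presented as estimates and 95% confidence intervals for differences in means". It does not mention a change score, an arm-by-scan term, adjustment for the first scan, a model of both scans, a way of judging persistence, or a method for missed scans. Section 4.7.2 expects that some infants will not be scanned, through death, instability or withdrawal.

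**The concern.** Persistence involves two time points, and the analysis section handles outcomes without reference to time. If each scan is analysed separately, which is the natural reading of section 4.11.2 although it is not stated, the report will contain two arm differences, each with its own interval. Those two intervals do not yield an interval for the change between scans. That needs the within-infant covariance, which separate analyses do not use. A statement that an effect persisted, shrank or grew would then have no estimate of precision behind it.

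The second issue is missed scans. A separate analysis at term plus 6 weeks uses only infants scanned at that visit. An infant scanned at term but not later contributes nothing to it, although the first scan carries information about the likely second value. Section 4.11.1 sizes the trial to 66 scans at term and allows for no further loss before the second scan.

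**Working it through.** **Inputs from the documents.** Section 4.11.1 gives the mean and SD of adiposity at term, "using whole body MRI is 0.677(0.243)l", and the design target: "A sample size of 22 infants in each group would enable us to detect a 0.243l difference in adiposity between groups". It also gives a smaller difference of 0.096 l, Bonferroni correction in Table 3, 10% mortality, 10% dropout, and recruitment of 2 to 4 infants per month for 18 months.

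**Assumptions, because the documents give no figure.** Between-scan correlation ρ of 0.5 to 0.8; the same SD at both scans; 20% of first-scan infants missing the second scan, as an illustration.

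**1. The plan's own figure.** The standard error (SE) of one pairwise difference at 22 per arm is 0.243 × √(2/22) = 0.0733 l. By the normal approximation, power for 0.243 l is 82.2% at two-sided α = 0.05/3 and 82.4% at α rounded to 0.017. Table 3 prints 82.4% for a total of 66, so the SE matches the plan's own calculation.

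**2. Precision of the change in arm difference.** SE(change) = 0.0733 × √(2(1 − ρ)).

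| ρ | SE of change (l) | 95% CI half-width (l), SE × 2.018 (t, 42 df) |
|---|---|---|
| 0.5 | 0.073 | 0.148 |
| 0.7 | 0.057 | 0.115 |
| 0.8 | 0.046 | 0.094 |

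Combining two separate estimates as if they were independent would give 0.0733 × √2 = 0.104 l, which is too large throughout this range.

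**3. Gain when second scans are missed.** Let V be the variance of the second-scan difference with nobody missing, and m the fraction who miss it.
- Second-scan data alone: V/(1 − m).
- Joint model of both scans: V × [1 + (m/(1 − m)) × (1 − ρ²)] = V × (1 − mρ²)/(1 − m).
- Ratio of joint to separate: 1 − mρ².

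With m = 0.2 the ratio is 1 − 0.2 × 0.25 = 0.95 at ρ = 0.5, and 1 − 0.2 × 0.64 = 0.872 at ρ = 0.8. The variance falls by 5 to 13%, and the SE by about 2.5 to 7%.

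**4. How often separate tests would disagree although the effect is constant.** This was simulated for one pairwise contrast with the same true difference at both scans, using the SE from step 1 and a two-sided t test on the pooled three-arm degrees of freedom (63 at 22 per arm). The last two columns give the chance that the second scan is not significant, given that the first is; ranges run from ρ = 0.8 to ρ = 0.5.

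| Scanned per arm | True difference (l) | Unadjusted 5% | Bonferroni 0.05/3 |
|---|---|---|---|
| 22 | 0.243 | 5–7% | 9–14% |
| 22 | 0.096 | 33–52% | 41–64% |
| 10 | 0.243 | 18–29% | 26–42% |

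The 10-per-arm row is the low end of the stated recruitment: 2 × 18 = 36 infants, 12 per arm, and 12 × 0.8 = 9.6 scanned.

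**The case against.** The strongest reply is that the plan already answers the question it asks. Whether an arm difference is present at term plus 6 weeks is estimated directly by the randomised comparison at that age, and ignoring the within-infant correlation neither biases nor invalidates that comparison. Aim B speaks of magnitude at each age, and no section makes change between scans an objective. This stands. The added model is needed only for a statement about change, and to use infants with one scan more efficiently.

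A reader might go further and infer that the plan will judge persistence by whether the second scan is significant, so that a lasting effect can easily be reported as having faded. The documents do not support that. No section states such a rule, and section 4.11.2 commits to estimates with 95% confidence intervals. The percentages in step 4 are the error rate of a rule that the plan does not contain. Even under that rule, the rate at the design difference with full accrual is 5 to 7% at the unadjusted level. It becomes substantial only at smaller effects or lower recruitment, though section 4.11.1 itself tabulates the 0.096 l difference and expects the trial to be underpowered for adiposity.

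It is also fair to say that the added contrast will not settle the matter. With a half-width of 0.094 to 0.148 l, it can barely separate persistence from complete loss of a 0.096 l effect at ρ = 0.8, and cannot at ρ = 0.5. A simple change score would supply a contrast too, although only from infants with both scans.

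Finally, no loss between scans is stated, so the gain in step 3 depends on an assumed 20%. Nor does the plan say that it will use complete cases; it gives no method for missing scans.

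**Conclusion.** The omission is real and minor. The second scan has a stated purpose of examining persistence, and the analysis section names nothing that links it to the first. The comparison at term plus 6 weeks is sound for whether a difference exists then. What is missing is an interval for the change in arm difference, and any use of first-scan data for infants who miss the second.

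With ρ of 0.5 to 0.8 and equal SDs, both assumed, the SE of the change is 0.073 to 0.046 l at 22 per arm. The variance of the second-scan estimate would be 5 to 13% lower if 20% miss that scan. These are modest gains on a secondary outcome in a study that describes itself as primarily a feasibility pilot. The primary outcome and its analysis are unaffected.

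**What to change.** In section 4.11.2, keep the primary analysis at term equivalent age as it is, and add one model of total body adiposity using both scans. Its terms would be arm, scan, arm-by-scan and the same baseline covariates as the primary model, with an unstructured within-infant covariance. Report, for each pair of arms, the difference at each scan and the change in that difference between scans, each with a 95% CI. State that any claim that an effect persists or fades will rest on these estimates, and that loss of significance at the second scan is not evidence of fading.

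The cost is a few sentences and one model, with no new data or infants. There are two downsides to state openly. The model assumes that missed scans are missing at random given the observed data, which may be doubtful where infants are too unstable to scan. And the interval for the change will be too wide to resolve a 0.096 l change unless the correlation is high, about 0.8 or more at 22 per arm.

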2.1 Summary

Mother's Own Milk (MOM) is believed to confer many benefits for preterm babies. However, on average, mothers giving birth preterm are able to provide less than half their baby's milk requirements. In these circumstances standard clinical practice is to make up the shortfall in MOM with either pasteurised Human Donor Milk (HDM) or Preterm Formula (PTF). Pasteurisation reduces or destroys many biologically active components; human milk, unlike PTF, is very variable in composition and despite fortification, there are concerns that preterm macronutrient requirements are not met with HDM. Doctors who use HDM to supplement insufficient MOM, do so primarily in the hope that despite pasteurisation of HDM, this strategy will reduce two feared conditions, bloodstream infection and necrotising enterocolitis, a serious inflammatory disease involving bacterial invasion of the bowel. The mortality from these conditions is high and survivors are at substantially increased risk of neurodisability. Metabolic advantages of human milk for preterm infants may also exist. Follow-up of preterm babies recruited to landmark nutritional trials in the early 1980s suggest positive effects of human milk on insulin sensitivity, blood pressure, and other metabolic outcomes. Doctors who prefer PTF to supplement insufficient MOM, believe this will benefit growth, including brain growth, and long-term neurodevelopment. Which of these two approaches is more efficacious and effective is unknown.

In order to address this crucial question, central to preterm newborn care, a multicentre UK-wide study randomising 4000 preterm babies would be necessary to achieve sufficient power to evaluate the impact on the short-term outcomes necrotising enterocolitis and bloodstream infection, and establish cohorts with power to address long-term growth and metabolic outcomes.

The objective of this PhD proposal is to conduct a pilot study to inform an application to the NIHR or other major funding body to conduct a randomised controlled trial designed to address cardinal short-term (necrotising enterocolitis, bloodstream infection) and longer-term outcomes (growth, obesity, insulin resistance), that would require the recruitment of approximately 4000 babies across sites throughout the UK. This pilot trial will not involve any novel intervention, it will merely randomise babies to three existing, widely used, standard feeding practices.

2.2 The knowledge gap

2.2.1 Human milk versus preterm formula: Necrotising Enterocolitis

Human milk not only provides nutrition, but is rich in biologically active molecules with advantages to infant host defence. Large nutritional trials of MOM versus PTF in the late 1980's showed that infants who received MOM were 5-10 times less likely to develop necrotising enterocolitis (NEC) than infants fed with PTF, where both MOM and PTF were sole diet (1). A meta-analysis of seven trials in the 1970's and 1980's each comparing HDM with PTF for preterm infants (2), suggested that HDM given as a sole diet is associated with a lower risk of NEC compared with formula. However, in these trials, the total sample size was small, the methodological quality poor, and their nutritional protocols did not evaluate the currently widely used bovine human milk fortifiers, or contemporary preterm formulas. A more recent Cochrane meta-analysis has failed to show any such protection against NEC with HDM compared to PTF when used to supplement MOM (3). Furthermore, only one trial has ever compared bovine fortified

HDM with PTF, in which no significant differences in mortality or NEC was found (4). These uncertainties are reflected in the varying attitudes of staff, parents and countries to HDM (5). The lack of good evidence of efficacy of HDM led the National Institute for Clinical Excellence to refrain from advising on clinical indications in their guidance "Donor breast milk banks: the operation of donor milk bank services" (NICE 2010).

2.2.2 Human milk versus preterm formula: metabolic consequences

The association between low birth weight and later adult metabolic disease such as type-2 diabetes is now well established (6,7). Epidemiological studies show an association between low birth weight and decreased lean mass, increased total adiposity, and increased central adiposity in adults (8) ,a body composition which has consistently been linked with later insulin resistance (9). Third trimester and early postnatal growth appears to have a major impact on this later adult metabolic phenotype. Longitudinal growth data indicate that those born small for gestational age but then show catch up growth, specifically from birth to 3 months, are most at risk of later insulin resistance in young adulthood (10)

Prematurity, regardless of fetal growth, has been associated with later insulin resistance in adults (11). Using whole body MRI, our group has shown that the preterm born adult phenotype is characterised by increased total and abdominal adiposity compared to term born controls (12). As early as at term equivalent age we have shown that there is aberrant deposition of adipose tissue, with an excess of intra-abdominal adipose tissue, and reduced lean body mass in preterm infants in comparison to their term-born counterparts, with illness severity being the major determinant of adiposity (13). Although the neonatal morbidities associated with preterm birth may well contribute to long term metabolic health, mounting evidence highlights the impact of early growth velocity during postnatal third trimester growth.

Follow-up to early adulthood of preterm babies recruited to landmark nutritional trials in the early 1980s by Lucas and colleagues showed lower insulin resistance at adolescence in preterm infants randomised to receive standard formula compared to a growth promoting enriched formula (14) , those infants with the greatest growth velocity in the first 2 weeks of life having the greatest insulin resistance at adolescence. Consistent with these findings, Roteveel et al have recently shown that preterm infants who had highest early postnatal growth velocities had highest insulin resistance as young adults regardless of prior fetal growth (15).

In parallel trials Lucas and colleagues showed positive effects of human milk on insulin sensitivity, blood pressure, and other metabolic outcomes (16-19). Whether the observed metabolic advantages with human milk are due to its unique bioactive properties, or result from a protective slower early growth as compared to preterm formula, remain unclear (20). This pilot trial will begin to address this question by comparing fortified and unfortified HDM with PTF.

Increased adiposity could be a plausible mechanism by which manipulation of early postnatal nutrition may predispose to poor metabolic health in preterm born adults. Nutritional differences are key causal candidates for poor metabolic health: the diet of the preterm neonates in intensive care is high in fat and carbohydrate and low in protein. This is in marked contrast to third trimester intrauterine diet which is high in amino acids, moderate in glucose and low in lipid (21). But within this preterm diet, human milk may attenuate this adiposity: an observational study of an indirect measurement of body composition using dual energy x-ray absorptiometry (22) has shown increased fat mass in preterm babies at discharge when PTF was used compared to fortified HDM, in supplementing MOM. Using dual energy x-ray absorptiometry in a cohort of preterm infants recruited just before discharge, Cooke et al (23) showed that

infants randomised to receive PTF or term formula had increased total non-fat and fat mass but not percentage fat mass, at 3,6, and 12 months corrected age, compared to breast fed preterm controls. In contrast to the pattern of adiposity that we observed, changes in fat mass were explained by increased fat accretion in the legs rather than centrally. However, no studies to date have examined the impact of feeding preterm infants from birth, on changes in adiposity quantity and distribution, at discharge and post-discharge.

Emergence of insulin resistance has been shown to parallel that of central adiposity at age 2-4yrs in SGA infants who show catch up growth (24). Insulin resistance in this growth pattern correlates with growth velocity immediately after birth (10) and has been shown as early as 1yr of age, in a cohort of SGA infants who gained one birth centile in weight in the first year (25). The “gold standard” for measuring insulin resistance is the euglycaemic hyperinsulinaemic insulin-glucose clamp technique which cannot be used during infancy, but a surrogate marker of insulin resistance, a logarithmic transformation of the fasting insulin and glucose concentration (Quantitative Insulin-sensitivity Check Index, QUICKI (26) has been validated in children and adults, and has been measured in preterm infants shortly after birth in a handful of studies (27,28). Yet as far as we know there are no prospective studies assessing direct measurements of adipose tissue distribution with growth and markers of insulin resistance in the first few weeks and months of life.

Our group has also shown increased intrahepatocellular lipid (IHCL) content in preterm infants at term compared to healthy term infants (29). Raised IHCL is closely associated with abdominal adiposity (30), obesity, and dyslipidaemia. Recent work by Nobili et al (31), showed that breast feeding had a protective effect, in a dose dependent manor, on progression of non-alcoholic fatty liver disease in a sample of children diagnosed with the disease in a paediatric liver unit. Although there are several possible determinants of raised IHCL in the preterm infant, the impact of human milk warrants further investigation.

Metabolic “profiles” can now be measured using small volumes of biological tissues and fluids, such as dried blood spots, urine and stool. Analysis is carried out using high throughput nuclear magnetic resonance (NMR) spectroscopy, which provides the opportunity to analyse a large number of metabolites simultaneously and therefore offers extensive scope to study metabolic responses in relation to normal development, disease, physiological variation, nutritional intake and medications (32). A small number of reports describe metabolic profiling in newborns and demonstrate the feasibility of this technique in detecting differences in metabolic responses to preterm birth (33).

Yet there remains no randomised controlled enteral nutritional trial in preterm infants from birth to discharge and beyond with direct measures of body composition, QUICKI, IHCL or metabolomic profiling as the outcome. Furthermore, no long term follow up of such early preterm body composition, IHCL and metabolomic phenotypes exist, making any nutritional mechanistic pathways to poor adult metabolic health difficult to define.

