4.6 Randomisation

Randomisation will be generated centrally using a computer program, with minimisation by infant sex, gestational age (25-27+6 wks, 28-31+6 wks) birth-weight Z score (<-1.28, >-1.28) Randomisation will take place between 24-48hrs of age. Infants will be randomised to receive either HDM or PTF to make up any shortfall in Mother's Own Milk (MOM) until 34+6 weeks postmenstrual age. Blinding of the intervention is not practicable because of the distinctive appearances of human milk and formula, and the method of administration to preterm babies by syringe and nasogastric tube. At 35 weeks, the infant will be close to discharge, and feeding will be directly from the breast or formula by bottle in accordance with maternal choice.

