4.9.5 Daily evaluations

Performed daily until discharge from NICU

- Record nutritional intake (parenteral nutrition, daily volume of MOM, daily volume of trial feed – all collected on case report form)
- Record level of care (BAPM 2001 criteria)
- Record if infant is nil by mouth and reason for this (collected on case report form)
- Record of withdrawal information (collected on case report form)
- Weight (when on parenteral nutrition)

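### Illness severity, which the protocol ranks as the major determinant of adiposity, is not named in the minimisation or the analysis; pre-specifying a pre-allocation measure of it is an optional, low-cost gain in precision

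*Combined protocol and SAP*

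**What the plan says.** - **Background (2.2.2).** Describing the group's own findings at term equivalent age, the protocol reports abnormal fat deposition in preterm compared with term-born infants, "with illness severity being the major determinant of adiposity (13". It gives no effect size, severity measure or time of measurement.
- **Allocation (4.6).** Allocation is generated centrally, "with minimisation by infant sex, gestational age (25-27+6 wks, 28-31+6 wks) birth-weight Z score (<-1.28, >-1.28". On timing: "Randomisation will take place between 24-48hrs of age". The trial is unblinded.
- **Analysis (4.11.2).** Outcomes are to be analysed by "multiple linear regression with adjustment for covariates where appropriate". Sex, gestational age and birth-weight z score are treated as dealt with by the stratification, "while those such as ethnicity will be adjusted for". The null hypothesis is handled separately: "differences between groups will be tested using ANOVA, with examination of the 3 pairwise differences". No covariates are mentioned for that test.
- **Data.** The baseline list (4.9.4) has no severity score, only unspecified medical conditions. Section 4.9.5 has a daily item: "Record level of care (BAPM 2001 criteria". That item is not marked as case report form data, so under 4.9.1 it comes from the national database, which is built from point-of-care records on all admissions.
- **Sample size (4.11.1).** In the group's database of preterm infants at term equivalent age, "the mean (standard deviation) of directly measured total body adiposity, using whole body MRI is 0.677(0.243)l". The target is 22 scanned infants per arm.

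**The concern.** Total body adiposity at term equivalent age is the primary outcome. The protocol singles out one determinant of adiposity at that age, then names it in neither the allocation nor the analysis. Two things follow.

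First, precision. Whatever share of the outcome variance a pre-allocation severity measure explains stays in the residual if the comparison is an unadjusted ANOVA. Aim B of section 3 is to estimate the magnitude of effect, and 4.11.1 concedes that the study will probably be underpowered for this outcome, so interval width matters.

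Second, the open covariate wording. In an unblinded trial it leaves the choice of covariates until data are visible. It also does not exclude severity summarised over the whole stay, such as intensive care days, necrotising enterocolitis or bloodstream infection. Those follow allocation. Section 2.1 says that donor milk is used mainly in the hope of reducing the last two. Adjusting the randomised comparison for them could remove part of a real feeding effect.

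**Working it through.** **Inputs.** From 4.11.1: SD 0.243 l, 22 scans per arm, three arms, 5% significance, Bonferroni correction for Table 3. Assumed, because the documents give no figure: the proportion R² of residual variance explained by the severity covariate, taken as 10%, 20% and 30%. A three-level care category (intensive, high dependency, special) costs 2 degrees of freedom.

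**1. The plan's own power.** For a 1 SD difference with two-sided alpha 0.05/3 (the divisor is inferred), normal approximation:

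Power = Φ(√(22/2) − z) = Φ(3.317 − 2.394) = 82.2%, against 82.4% in Table 3.

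The detectable difference at 80% power is (2.394 + 0.842) × 0.243 × √(2/22) = 0.237 l, as in Table 3. The plan's figures reproduce. They use the overall SD, with no covariate adjustment described, so variation due to severity is already in them.

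**2. Unadjusted interval.** SE = 0.243 × √(2/22) = 0.0733 l. With 66 − 3 = 63 df, t = 1.998, and the 95% half-width for a pairwise difference is 1.998 × 0.0733 = 0.146 l.

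**3. Adjusted interval.** Half-width = t(61) × 0.243 × √(1 − R²) × √(2/22) × √(1 + 2/61), with t(61) = 2.000. The last factor is the average cost of estimating two more coefficients. The equivalent increase in scans is (0.146 / adjusted half-width)² − 1, from unrounded values.

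| Assumed R² | Residual SD (l) | Half-width (l) | Equivalent extra scans |
|---|---|---|---|
| none (unadjusted) | 0.243 | 0.146 | – |
| 10% | 0.231 | 0.141 | 7% |
| 20% | 0.217 | 0.133 | 21% |
| 30% | 0.203 | 0.125 | 38% |

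**4. Break-even.** Setting the adjusted half-width equal to the unadjusted one gives R² = 1 − (1.998/2.000)² / (1 + 2/61) ≈ 3.3%. Below that, adjustment widens the interval slightly; at R² = 0 the half-width is 0.149 l.

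**5. Chance imbalance.** Without adjustment, the part of a pairwise difference that comes from chance imbalance in the covariate has SD √R² × 0.0733 = 0.023, 0.033 or 0.040 l for the three R² values. This is a component of the 0.0733 l standard error, not an addition to it.

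**6. Timing.** Allocation takes place no earlier than 24 h of age. The calendar day of birth ends within 24 h of birth, so a level of care recorded for that day precedes allocation. Totals or events over the stay do not.

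**The case against.** **A reader might infer that the primary model leaves severity out.** The text does not settle this. The regression wording is open and ethnicity is only an example, so severity could be included. What the documents support is that no severity covariate is pre-specified and that the ANOVA has no stated covariates.

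**A reader might infer that the main source of outcome variation is left in the error term.** The support is one background clause in a sentence comparing preterm with term-born infants and stressing intra-abdominal fat and lean mass. It does not show how much of the variation in total adiposity severity explains among infants of 25+0 to 31+6 weeks. This objection stands, and it is why R² is only an assumption.

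**A reader might infer that imbalance biases the result or that the sample size is wrong.** Neither follows. Under randomisation, imbalance is already reflected in the standard error, and the stated power reproduces from an SD that includes it.

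**The proxy may be weak.** If severity in 2.2.2 reflects the neonatal course, most of it arises after allocation and cannot be used here. Level of care on one day is coarse, may vary little in this population, and overlaps with gestational age, which is already a minimisation factor. This also stands: the low end of the range is the more likely gain, and a small loss is possible.

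**It is a feasibility pilot.** True, and this limits the consequence. It does not remove the case for ruling out adjustment for severity measured after allocation.

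**Conclusion.** The point holds as an optional, low-cost improvement, not as an error in the design. The determinant that the protocol itself ranks first is not named in the minimisation or the analysis, and the covariate wording neither requires a pre-allocation measure nor excludes a post-allocation one.

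The gain depends wholly on an R² that the documents do not give. At 10% the half-width narrows by 0.005 l (about 3.5%); at 30%, by 0.022 l (about 15%). These figures apply R² to the full SD of 0.243 l. If other covariates had already reduced the residual SD, all the half-widths would shrink together and the proportional gain would be much the same. The argument against adjusting for whole-stay severity does not depend on R².

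**What to change.** In 4.11.2:

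1. State that the primary comparison of total body adiposity at term equivalent age is a linear model with terms for arm and pre-specified covariates, replacing the unadjusted ANOVA. The overall test and the three pairwise differences then come from the same model.
2. Name one severity covariate fixed before allocation, for example BAPM 2001 level of care on the day of birth, taken from the database already in use.
3. State that no severity measure recorded after randomisation (for example total intensive care days, necrotising enterocolitis or bloodstream infection) enters the randomised comparison. Any such analysis would be labelled exploratory.

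The cost is a few sentences and 2 degrees of freedom, with no extra infants, visits or data collection. Before fixing the choice, the group could use its existing preterm MRI database, if level of care is held there, to check whether the proxy explains more than about 3% of the variance.
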